8.2.3 Additional Secondary Efficacy Analyses

Refer to Section 8.2 for analysis sets and presentation of summary statistics. The Additional Secondary Endpoints will be assessed and presented at the nominal 5% level, i.e., there will be no alpha control applied at the planned analyses as described in Section 4. These endpoints are PFS, Biochemical Response (PSA response endpoints, LDH and ALP assessments), Health-related QoL, and Health Economics. Analysis will be performed on the PFS-FAS population

8.2.3.1 Progression-free Survival Analysis

PFS (defined in Section 8.1.3), will be summarized and analyzed in the same manner as those described for the alternate primary endpoint rPFS using the PFS-FAS, except using 2 sided p-values from the Cox regression model instead of the p-value from the Log-Rank test. Radiographic progressions per independent central review will be used. No sensitivity analyses will be performed for PFS. Additionally, the following will be presented:

- Number and % of PFS events that are due to death, radiographic progression, clinical progression (including the primary criteria of clinical progression), and PSA progression

8.2.3.2 Biochemical Response Analysis

All biochemical response analyses will be performed using the PFS-FAS. PSA, ALP, and LDH values will be summarized descriptively as follows:

- Continuous variable summary statistics for baseline, each time point, and % change from baseline for each treatment arm
- Plots of the mean (\pm standard error) values over time for PSA, ALP, and LDH.
- Summary statistics of PSA doubling time with 95% CI for the mean PSA doubling time
- Summary statistics of maximum % change from baseline
- Categorical variable summary statistics and 95% CIs of PSA response ($\geq 50\%$ decrease and PSA $\geq 80\%$ decrease)
- Waterfall plot of the maximum % change from baseline in PSA for each patient
- Duration of PSA response ($\geq 50\%$ decrease) will be presented descriptively the same as DOR (Section 8.2.2).

Unscheduled labs will not be included in tables but will be provided in listings.

Treatment arm differences of % change from baseline in PSA, ALP, and LDH across all time points will be analyzed using mixed effects general linear models for repeated measures, under the assumption of Missing at Random (MAR). The fixed effects will include treatment arm, time (as a categorical variable), treatment by time interaction, and randomization stratification factors. An unstructured variance-covariance matrix for the repeated measures for a single patient will be used. In case of problems with fitting the model, as an alternative, a heterogeneous Toeplitz and AR(1) structures will be considered to reduce the number of parameters of the model. If necessary for the model fit, the outcome variables might be transformed. Details of any transformations used will be provided in the CSR. The differences in least square means between the treatment arms and corresponding 95% confidence interval at selected time points will be presented.

For PSA response, analyses will be the same as those described for binary outcome ORR (Section 8.2.2).

Duration of PSA response will be analyzed using a mixture distribution analysis, as described for DOR (Section 8.2.2).

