3.2 Randomization and Blinding

Eligible patients will be randomized by an interactive response technology (IRT) system in a 2:1 ratio to the investigational treatment arm or the BSC/BSoC -only arm using a permuted block scheme. The approximate 30 eligible patients included in the sub-study will not undergo randomization as all patients will receive the investigational treatment arm. Randomization will be stratified by the following factors:

- LDH (≤ 260 IU/L vs. > 260 IU/L)
- Presence of liver metastases (yes vs. no)
- ECOG score (0 or 1 vs. 2)
- Inclusion of NAAD in best supportive/best standard of care at time of randomization (yes vs. no)

The study is open-label. However, access to subject treatment allocation will be limited to those individuals whose roles require access to perform their study responsibilities. Details of what roles and which individuals have access to unblinded data will be documented in a separate Data Access Plan maintained by the sponsor. Dates of access and reason for accesses will be recorded. Sponsor statisticians will be blinded and contract research organization (CRO) statisticians assigned to the study will be unblinded.

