Change from baseline in utility score will also be analyzed using general linear models for repeated measures. Baseline value (as a continuous variable), treatment arm, time (as visit number), treatment by time interaction, baseline by time interactions, and randomization stratification factors as main effects will be the fixed factors. A general (unstructured) variance-covariance matrix for the repeated measures for a single patient will be used. In case of problems with fitting the model, as an alternative, a heterogeneous Toeplitz and AR(1) structures will be considered to reduce the number of the parameters of the model. The differences in least square means between the treatment arms and corresponding 95% confidence interval at selected time points will be presented.

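### The PSA, ALP and LDH repeated-measures models use untransformed percent change, with no continuous baseline term and an open-ended transformation clause, and so give up precision, chiefly for PSA through the skewed scale.

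*SAP*

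**What the plan says.** SAP 8.2.3.2 sets up mixed models for repeated measures for "Treatment arm differences of % change from baseline in PSA, ALP, and LDH across all time points". Of the model terms it says: "The fixed effects will include treatment arm, time (as a categorical variable), treatment by time interaction, and randomization stratification factors". The covariance is unstructured, with simpler structures as fallback, and data are assumed missing at random. On scale it adds: "If necessary for the model fit, the outcome variables might be transformed", followed by "Details of any transformations used will be provided in the CSR". The analysis set is the PFS-FAS, and the output is differences in least-squares means with 95% intervals at selected time points.

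Three other places bear on this:

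- SAP 8.2.3.3.1 models change in the EQ-5D utility score with "Baseline value (as a continuous variable), treatment arm, time (as visit number), treatment by time interaction, baseline by time interactions" among the fixed factors. SAP 8.2.3.3.2 and 8.2.3.3.3 carry that model over to FACT-P and BPI-SF.
- SAP 5.6 and 8.1.3 compute PSA doubling time from a linear model on the natural log of PSA.
- SAP 3.2 lists LDH, cut at 260 IU/L, among the four stratification factors. PSA and ALP are not stratification factors.

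SAP 8.2.3 places these analyses among the additional secondary endpoints, at a nominal 5% level without alpha control.

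**The concern.** Percent change is lopsided. The best possible response is -100%, while a hypothetical rise from 2 to 40 ng/mL is (40 - 2)/2 = +1900%; protocol inclusion criterion 11a accepts PSA progression from a start value of 2.0 ng/mL. A normal-theory model on that scale gives a handful of rising patients a large say in the arm means and in the residual variance. Leaving out the continuous baseline discards prognostic information that is already collected. The transformation clause might repair the scale, but it names no transformation and no criterion. The choice would be made after looking at the fit, in an open-label trial whose CRO statisticians are unblinded (SAP 3.2).

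What is at stake is the precision and robustness of the longitudinal comparison of the three markers. No primary or key secondary conclusion depends on it.

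**Working it through.** The plan states no power, SD, correlation or effect size for these models, so there is no figure of its own to reproduce.

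**Inputs from the documents.** The expected PFS-FAS is about 557 patients (SAP 3.4) and allocation is 2:1 (SAP 3.2), so 557 × 2/3 ≈ 371 against 186. Tests are two-sided at 5% (SAP 5 and 8.2.3).

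**Assumed inputs.** Markers are log-normal, with a treatment effect that is additive on the log scale. Log-scale SDs at baseline and follow-up are 1.5 and 1.7 (PSA-like) or 0.6 and 0.65 (ALP- or LDH-like). The baseline to follow-up correlation ρ runs from 0.5 to 0.9.

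**Step 1: cost of omitting baseline on the log scale.** With equal SDs, a change score has variance 2σ²(1 - ρ) and the baseline-adjusted estimate σ²(1 - ρ²). The ratio is 2/(1 + ρ): 1.33, 1.18, 1.11 and 1.05 at ρ = 0.5, 0.7, 0.8 and 0.9. If the adjusted analysis has 80% power, the unadjusted one has Φ(2.80 × √((1 + ρ)/2) - 1.96) = 68%, 73%, 76% and 78%.

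**Step 2: scale and covariate together.** One post-baseline visit was simulated, with 2,000 data sets per row. The effect was set so that the log ratio with log baseline has about 80% power. Entries are power in percent. The last column is the median share of the residual sum of squares, under the SAP default, carried by the 6 most extreme of 557 patients.

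| Marker, ρ | % change (SAP default) | % change + log baseline | log ratio | log ratio + log baseline | top 6 share |
|---|---|---|---|---|---|
| PSA-like, 0.5 | 34.6 | 35.6 | 71.7 | 80.4 | 72% |
| PSA-like, 0.7 | 48.6 | 49.0 | 76.6 | 79.1 | 57% |
| PSA-like, 0.8 | 59.7 | 60.0 | 80.6 | 81.7 | 45% |
| PSA-like, 0.9 | 69.8 | 69.8 | 79.8 | 79.6 | 32% |
| ALP/LDH-like, 0.5 | 64.4 | 72.4 | 72.2 | 80.4 | 26% |
| ALP/LDH-like, 0.7 | 73.8 | 76.4 | 77.2 | 80.1 | 20% |
| ALP/LDH-like, 0.8 | 75.2 | 76.2 | 78.4 | 79.8 | 17% |
| ALP/LDH-like, 0.9 | 78.6 | 79.0 | 79.9 | 80.2 | 14% |

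Loss from the SAP default to the last model:

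- PSA-like: 80.4 - 34.6 = 45.8 points at ρ = 0.5, down to 79.6 - 69.8 = 9.8 at ρ = 0.9.
- ALP/LDH-like: 80.4 - 64.4 = 16.0 points, down to 80.2 - 78.6 = 1.6.

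**Step 3: which part does the work.** For PSA-like data at ρ = 0.5, changing the scale alone gains 71.7 - 34.6 = 37.1 points; adding baseline to percent change gains 35.6 - 34.6 = 1.0. For ALP/LDH-like data at ρ = 0.5 the two are about equal: 72.2 - 64.4 = 7.8 for scale and 72.4 - 64.4 = 8.0 for baseline.

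**Step 4: larger effects.** The same PSA-like simulation with a true 50% reduction gives 80%, 98%, 100% and 100% power for the SAP default at ρ = 0.5, 0.7, 0.8 and 0.9, against 100% throughout for the log ratio with log baseline. With a 25% reduction and ρ = 0.8 the figures are 69% and 88%.

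**Step 5: type I error.** With no effect, the SAP default rejects in 4.4% to 5.8% of data sets over the eight settings (Monte Carlo standard error about 0.5 points).

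**The case against.** The strongest reply is that the effect on PSA may be large enough for the scale not to matter. Protocol 1.1 cites a PSA reduction of at least 50% in 64% of patients in the prospective phase 2 study of this drug, against declines above 50% in 4% to 22% with a second hormonal agent. In a simulation with 300 against 150 patients, response proportions of 64% and 22% gave 99% to 100% power on either scale. At 40% and 22%, percent change had 95% to 98% power at log SD 1.0 to 1.2, but 81% at SD 1.7, against 100% for the log ratio. This stands: for PSA the loss can be nil, though not under wide spread and weak correlation.

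Further points stand in part:

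- The SAP does permit a transformation, tied to model fit and not to the treatment effect, and reports it in the CSR. That softens the charge of a data-driven choice. It does not make the transformation pre-specified.
- Percent change already divides by baseline, and the utility-score model concerns absolute change in a bounded score. The contrast shows that baseline adjustment is familiar practice in this SAP; it is not a contradiction.
- Percent change suits the 50% and 80% thresholds and the waterfall plot. That is a reason to keep it for display.

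A reader might also infer that the missing covariate is what costs PSA its power. Step 3 shows otherwise. Nor is it exact to say that no baseline enters at all: LDH does, coarsely, through its stratum.

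**Conclusion.** The point holds as one of efficiency and robustness. For PSA the right-skewed scale is the main cause of lost precision. For ALP and LDH the loss is small to moderate, and scale and missing baseline both contribute. When the better model has about 80% power, the loss is about 10 to 46 points for PSA-like data and 2 to 16 points for ALP- or LDH-like data; at large PSA effects it falls to nil when ρ is 0.8 or more.

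These sizes rest on assumed SDs and correlations, and on a single visit without strata or missing data. The simulation generates log-normal data, which favours the log model by construction. The direction is more secure than the size.

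Two stronger readings are not supported. One is that the tests are invalid: type I error stays near 5%, and coverage under a real effect was not examined. The other is that the biochemical response endpoint is compromised: the responder comparison (confirmed decrease of at least 50%) is a separate logistic regression under SAP 8.2.3.2 and is untouched. With a nominal 5% level and no alpha control, this is an improvement worth making, not a defect that threatens a trial conclusion.

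**What to change.** In SAP 8.2.3.2, name log(post/baseline) as the response for each marker. Add log baseline and log baseline-by-time to the fixed effects already listed, and delete the optional transformation sentence. Report back-transformed geometric mean ratios between arms with 95% intervals at the selected time points. Keep percent change for the descriptive tables and the waterfall plot. State that the rule in SAP 9.3 for values below the detection limit applies to PSA as well, so that every log is defined.

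The cost is SAP wording and a small programming change; no new data are needed. The one drawback is that the model estimates become ratios and not mean percent changes. A ratio of 0.75, for example, reads as a 25% lower geometric mean relative to control.

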8.2.3.3 Quality of Life (QoL) Analysis

For QoL analyses, patient reported outcomes (PROs) will be assessed using the questionnaires EQ-5D-5L, FACT-P, and BPI-SF.

Analyses will be done on the PFS-FAS, and all results will be reported by treatment arm. QoL measures are collected on Day 1 of each treatment cycle and at the EOT visit. Analyses over time will include time up through EOT visit.

For analysis of each outcome, only patients with a baseline value and at least one post baseline time point will be included. As with all efficacy analyses, main models will be adjusted for randomization stratification factors. Type I error is not controlled in the multiple health related QoL analyses. Thus, all p-values presented will be unadjusted and are nominal and descriptive.

8.2.3.3.1 EQ-5 Dimension-5 Level (EQ-5D-5L) Questionnaire

The EQ-5D-5L is shown in protocol Appendix 9. The higher the EQ-VAS score, the better the QoL. The higher the EQ-5D items, the worse the QoL.

Description and Scoring

The EQ-5D-5L consists of the EQ-5D descriptive system and the EQ visual analogue scale (EQ-VAS). The EQ-5D-5L descriptive system comprises the following 5 dimensions: mobility, self-care, usual activities, pain/discomfort, and anxiety/depression. The EQ-VAS records the respondent's self-rated health on a vertical, visual analogue scale.

Each of the five dimension-scales contain five levels, with level 1 indicating no problems, level 2 indicating slight problems, level 3 indicating moderate problems, level 4 indicating severe problems, and level 5 indicating unable to/extreme problems.

The EQ-VAS is scored by assigning an integer value, ranging from 0 (Worst imaginable health state) to 100 (Best imaginable health state), corresponding to the mark placed by the patient on the VAS. Ambiguous answers (e.g., two marks placed on the scale by a patient) should be treated as missing values.

Scale name	Number of items	Item range*
Descriptive System Dimension		
Mobility	1	1-5
Self-Care	1	1-5
Usual Activities	1	1-5
Pain/Discomfort	1	1-5
Anxiety/Depression	1	1-5
Health State Evaluation		
EQ-VAS*	1	0-100

* EQ-VAS is a continuous visual analog scale, with integer scores ranging from 0 to 100.

A utility score will be obtained by using a weighted combination of the levels of the five dimension-scales. The weights are based on value sets which are country-specific. The country specific code for the U.K. will be used for all sites in this study since the health economics modeling will target the U.K. population for developing the core economic model. Each patient's 5 digit health states code (response to question 1,2,3,4, and 5

concatenated (ex., 41325 results in a utility score of 0.193)) is converted to a utility score using the EQ-5D-5L value set, available in the cross-walk index value calculator which can be downloaded from the web site <https://euroqol.org/eq-5d-instruments/eq-5d-5l-about/valuation/crosswalk-index-value-calculator/>. (Scroll to the bottom of the web page and download the Excel file. Use the sheet labelled 'EQ-5D-5L Value Sets.')

Since utility score depends on the combination of all items' responses, any missing response results in a missing utility score. If a patient dies, for analysis he will be assigned a score of 0 on the date of death. In the U.K. value set, utility scores ranges from the lowest possible score for a living patient of -0.594 (when all responses are '5') to 1 (when all responses are '1').

Analysis

For each of the five dimension-scales, frequency count and percentage of each reporting level (1 to 5) over time will be presented.

Utility score and EQ-VAS, will be summarized as continuous variables and will be presented for each time point. For EQ-VAS and Utility score, a plot of the mean values with standard errors by treatment group at each time point (showing number of subjects at each visit), will be constructed.

The proportion of patients and associated 95% CI who experience any improvement relative to baseline in utility score (an increase of .001 or more) at any time up through EOT will be summarized for each treatment.

Similarly, the proportion of patients with worsening relative to baseline, indicated by no change or any decrease in score, will be summarized.

Time to worsening for utility score is defined as the time (in months) from randomization to the first occurrence of worsening in score relative to baseline (no change or any decrease), clinical disease progression (excluding radiographic and PSA progression), or death, whichever is earlier. If no event is experienced, the censoring date will be time of the last QoL assessment.

Survival curves for the time to worsening (months) for each treatment arm will be computed using the Kaplan-Meier method. The two treatment arms will be compared using a cox regression analysis stratified for randomization stratification factors (LDH \leq 260 UI/L vs \geq , liver metastases (yes vs no), ECOG (0-1 vs 2), Inclusion of NAAD in BSC/BSoc at time of randomization (yes vs no)). The 25th percentile of and median time to worsening will be presented, in case less than 50% of subjects experienced worsening for some variables.

Change from baseline in utility score will also be analyzed using general linear models for repeated measures. Baseline value (as a continuous variable), treatment arm, time (as visit number), treatment by time interaction, baseline by time interactions, and randomization stratification factors as main effects will be the fixed factors. A general (unstructured) variance-covariance matrix for the repeated measures for a single patient will be used. In case of problems with fitting the model, as an alternative, a heterogeneous Toeplitz and AR(1) structures will be considered to reduce the number of the parameters of the model. The differences in least square means between the treatment arms and corresponding 95% confidence interval at selected time points will be presented.

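### The utility of 0 assigned at death can count as an EQ-5D-5L improvement for a patient whose baseline utility is negative

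*SAP*

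**What the plan says.** SAP 8.2.3.3.1 sets these rules for the utility score:

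- **Score at death:** "If a patient dies, for analysis he will be assigned a score of 0 on the date of death".
- **Range:** with the U.K. value set, "utility scores ranges from the lowest possible score for a living patient of -0.594" up to 1, so a baseline below 0 is possible.
- **Improvement:** the proportion of patients "who experience any improvement relative to baseline in utility score (an increase of .001 or more) at any time up through EOT".
- **Worsening:** "the proportion of patients with worsening relative to baseline, indicated by no change or any decrease in score". Death is not named.
- **Time to worsening:** besides a score at or below baseline, the events are "clinical disease progression (excluding radiographic and PSA progression), or death, whichever is earlier".
- **By-visit summaries:** means are tabulated and plotted at each time point. Change from baseline goes into a repeated-measures model whose time axis is visit number. Neither description mentions death.

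SAP 8.2.3.3 limits the window ("Analyses over time will include time up through EOT visit"), requires a baseline and at least one post-baseline time point, and declares all quality-of-life p-values nominal and descriptive.

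**The concern.** The assigned 0 is lower than most living scores but higher than the worst ones. The improvement rule compares any score in the window with baseline and does not distinguish an observed score from an assigned one. A patient who starts below 0 can therefore be reported as having better quality of life because he died.

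The EQ-5D-5L outputs would then disagree with each other: the same death is a success in the improvement table and a failure in the time-to-worsening curve. That is hard to defend in a trial with high expected mortality, even for descriptive results.

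A second question concerns the means and the model. The 0 belongs to a calendar date, and no rule places it at a visit or carries it forward. If it were placed at a visit, those summaries would mix living and death values at that visit only.

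**Working it through.** The plan states no figure that depends on this rule, so there is none to reproduce. The check applies the SAP's rules as written.

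**1. Classification of a death.** Change = 0 - baseline. Improved if the change is 0.001 or more; worsened if it is 0 or less.

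| Baseline | Change at death | Improved | Worsened |
|---|---|---|---|
| -0.594 | +0.594 | yes | no |
| -0.300 | +0.300 | yes | no |
| -0.100 | +0.100 | yes | no |
| -0.001 | +0.001 | yes | no |
| 0 | 0 | no | yes |
| 0.193 | -0.193 | no | yes |
| 0.650 | -0.650 | no | yes |

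Every baseline from -0.594 to -0.001 turns the death into an improvement. For baselines of 0 or above, the rule gives the sensible answer.

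**2. When the death alters a patient's status.** Improvement is met by a qualifying rise at any time in the window, so the 0 adds a patient to the improved group only if all three conditions hold:

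- the baseline is negative;
- death falls up through EOT;
- no earlier living score had risen by 0.001 or more.

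The table classifies the death score alone. A patient with an earlier living score at or below baseline could also be in the worsening proportion through that score; his death would not put him there.

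**3. Size.** Patients added = N × q × d × (1 - e), where:

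- N = 557, the expected number randomized on or after 5 March 2019 (SAP 3.4). This is slightly too large, since a post-baseline time point is also required.
- q = share with a negative baseline; d = share of those dying up through EOT; e = share of those who had already improved on a living score. The documents give none of these.

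With e = 0, which gives the upper limit:

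- q = 1%, d = 5%: 557 × 0.01 × 0.05 = 0.3 patients (0.05%)
- q = 3%, d = 15%: 557 × 0.03 × 0.15 = 2.5 patients (0.45%)
- q = 5%, d = 30%: 557 × 0.05 × 0.30 = 8.4 patients (1.5%)
- q = 10%, d = 30%: 557 × 0.10 × 0.30 = 16.7 patients (3.0%)

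Any e above 0 reduces these counts. With e = 50% (also assumed), the last becomes 16.7 × 0.5 = 8.4.

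**4. Conditional: if the 0 is placed at a visit.** Assume 100 living patients at a mean of 0.70 and 5 deaths placed at that visit. The mean is (100 × 0.70 + 5 × 0)/105 = 0.667. At the next visit the zeros are gone and, if survivors are unchanged, the mean is 0.70 again. The numbers are invented and show only the mechanism.

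**5. Why the choice should be explicit.** Assume a survivor mean of 0.65 in both arms and exponential survival with medians of 10 and 13.7 months. (SAP 3.4 gives 13.7 months and HR 0.7306; 13.7 × 0.7306 = 10.0.) The survivors-only arm difference is 0. If 0 is carried to every later visit, the difference is 0.65 × (0.5^(t/13.7) - 0.5^(t/10)), which is 0.051 at t = 6 months and 0.071 at t = 12 months. This includes deaths after EOT, so it overstates what the planned window would show. The two summaries answer different questions.

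**The case against.** The other side has five good arguments.

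- **Negative baselines should be rare.** Protocol 4.1 requires ECOG 0 to 2 and life expectancy over 6 months, and Appendix 4b describes ECOG 2 as ambulatory and capable of self-care. The SAP's own example state, 41325, still scores +0.193. This stands and keeps the size small.
- **Many such patients would already have improved.** With a threshold of 0.001, an earlier living score may already qualify. This stands; the counts above are upper limits for their assumptions.
- **No inference depends on it.** The p-values are nominal, and time to worsening handles death correctly. This stands.
- **Death as 0 has an evident use.** Protocol 6.2.7 plans quality-adjusted life years from the EQ-5D. That explains the rule but does not justify its reach: SAP 8.2.3.4 leaves the economic analysis to a separate vendor, outside the SAP, while the 0 is assigned in the SAP's own analysis section without restriction.
- **The 0 may never reach a visit mean or the model.** SAP 5.1.2 summarizes by scheduled collection time, and its allowance for unscheduled quality-of-life evaluations does not clearly cover an assigned score. This stands.

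Because of the last argument, a reader might infer too much: that the mean curves will dip and rebound and that the model will be biased. The documents do not support that. They give the 0 a date but no visit number, so the effect exists only under one way of programming it. Nor do they show any resulting difference between arms.

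**Conclusion.** The misclassification follows directly from the SAP's rules. For a patient with a negative baseline and no earlier rise, death up through EOT creates an improvement, and the death itself does not count as worsening in the proportions. The same death is an event in time to worsening.

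The effect is small. Under the assumptions shown, it is at most about 0.3 to 17 of 557 patients, and probably towards the low end, because negative baselines should be rare and some of these patients will already have improved. Deaths in long-term follow-up fall outside the window. No confirmatory or time-to-worsening result changes.

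The point about the means and the model is conditional. If the 0 is placed at a visit, it enters once and then disappears; if not, those summaries are unaffected. The SAP does not say which. This is a minor correction, worth making because the result is wrong on its face and costs little to remove.

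**What to change.** In SAP 8.2.3.3.1:

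1. State that improvement is judged on scores reported while alive and that the assigned 0 is never an improvement. State that death up through EOT counts as worsening in the proportion worsened. The proportion would then agree with time to worsening in how it treats death.
2. Keep the assigned 0 out of the by-visit means and the repeated-measures model, and label both as describing patients while alive. FACT-P and BPI-SF already work this way: no score is assigned at death for them, and they use the same model. This does not fill in visits after death; it makes clear which question the summaries answer.
3. If a summary with death as 0 is wanted, make it a separate, labelled analysis with 0 carried to all later scheduled visits in both arms.

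The cost is a few SAP sentences and one change to a derivation. No data collection, sample size or confirmatory test is affected.
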